Both genistein and placebo tablets will be provided by DSM Nutritional Products Europe Ltd, Switzerland.

Other study intervention(s): The chemotherapeutic regimen for each subject will be determined by the treating physician and must contain a combination of at least two agents from the following list during each of the four cycles administered in this study: actinomycin, carboplatin, cisplatin, cyclophosphamide, daunorubicin, doxorubicin, etoposide, ifosfamide, topotecan.

Criteria for evaluation (i.e. endpoints):

Efficacy: To evaluate the effectiveness of genistein administration during myelosuppressive chemotherapy, the following endpoints will be compared between genistein cycles and placebo cycles:

Primary endpoint:

- Duration of grade 4 neutropenia, defined as an absolute neutrophil count (ANC) of < 500 cells/ μ l

Secondary endpoints (per cycle):

- Severity of neutropenia
- Duration of grade 4 neutropenia during hospital admissions for febrile neutropenia
- Frequency and duration of unplanned hospital admissions due to (an) adverse event(s)
- Days with fever (temperature > 101.5° F, or > 100° F more than once in a 24-hour period)
- Incidence and severity of infections
- Duration of antimicrobial agent use
- Duration and severity of oral mucositis
- Duration and severity of peripheral motor neuropathy (in subjects receiving vincristine)
- Incidence and severity of hearing impairment and tinnitus (in subjects receiving a platinum-based chemotherapy agent)
- Number of days delayed and percent reduction of full, planned doses of anti-neoplastic agents due to (an) adverse event(s)
- Incidence of primary and secondary G-CSF use
- Number of required blood product transfusions
- Cytokine, growth factor, C-reactive protein, and homocysteine levels as well as erythrocyte sedimentation rates

Safety: Safety will be assessed by incidence and severity of AEs and changes in physical examinations.

Statistical methods:

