5.1.7 Expected Adverse Events

The side effects of usage of genistein reported in the literature are mild. The most common effect is abdominal pain (≤ grade 2). This is the only AE that will be considered to be expected for the purposes of this study.

Genistein may have estrogenic properties. Therefore any condition which might be worsened by estrogen, such as breast cancer, uterine cancer, ovarian cancer, endometriosis or uterine fibroids, may also be worsened by administration of genistein. The effect of genistein in someone who is pregnant or breast-feeding is not known.

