6.2.1 Medical History and Physical Examination

A medical history must be obtained and physical exam performed during the Pre-treatment Assessment to establish baseline medical condition(s) ([Section 6.2](#)). Medical history includes clinically significant diseases, history of cancer (including date of diagnosis, location of disease, stage, grade, biopsies, resections, prior cancer therapies and procedures), and selected medications (anti-neoplastic agents, blood products, soy products, antimicrobials, and G-CSF) used by the patient within 28 days prior to protocol therapy (genistein/placebo).

A full physical examination will be performed at the Pre-treatment Assessment and Day 1 of each cycle ([Sections 6.2](#) and [6.3](#)). Physical examinations will include examination of the following body systems: general appearance/constitution (including height and body weight), skin, neck, HEENT (head, ears, eyes, nose and throat), cardiovascular system (auscultation of heart sounds), lungs/chest (auscultation of lung fields), abdomen palpation, genitourinary system (auscultation of bowel sounds), lymph nodes, extremities, and nervous system.

An abbreviated, symptom-directed physical exam will be performed at all other visits ([Section 6.3](#)). This must also be conducted in such a way to assess for incidence of secondary conditions listed as endpoints (i.e., infection, mucositis, etc.) In addition, any clinically significant abnormal finding which was not noted at the baseline assessment must be reported as an AE, provided it also meets the reporting criteria in [Section 9](#).

Baseline conditions and AEs must be reported as diagnoses, when possible. Laboratory value abnormalities present at the time of enrollment must be reported as baseline conditions according to their CTCAE classifications. The baseline onset and severity of all grades of all target AEs defined in [Section 6.2](#) must be reported, as well as any other

non-target baseline condition if its severity is greater than or equal to grade 3 ([Section 9.1.8](#)). The outcome of baseline conditions and resolution dates, when applicable, must be reported at the end of the follow-up period.

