- If ANC is < 500 cells/ μ L at any point after beginning weekly testing, resume twice weekly testing until ANC ≥ 500 cells/ μ L.
- ANC will be obtained daily during any admission for febrile neutropenia.
- All ANC values will be reported.
- Serum CRP, homocysteine, and ESR: Report raw data collected on Day 1 of Cycles 2, 3, 4, and the last day of Cycle 4
- Cytokine Panel and Isoflavone Panels: Draw and process specimen per the Procedure Manual on Day 1 of Cycles 1, 2, 3, 4, and the last day of Cycle 4
- Weight and height on Day 1 of each cycle
- The following **target AEs** must be assessed and the maximum grade reported for each cycle in addition to standard AE/SAE reporting ([Section 9](#)):
 - Neutropenia
 - Febrile neutropenia, with maximum associated temperature per cycle
 - Fever, including number of days per cycle, for temperatures $> 101.5^{\circ}$ F, or $> 100^{\circ}$ F more than once in a 24-hour period (report maximum temperature)
 - Infections and Infestations: Maximum grade for any AE listed in this CTCAE category. Infections meeting the AE reporting threshold must be listed individually.
 - Oral mucositis
 - Tinnitus (subjects receiving platinum-based chemotherapy only)
 - Hearing impairment (subjects receiving platinum-based chemotherapy only)
 - Peripheral motor neuropathy (subjects receiving vincristine only)
- Report per cycle:
 - Study supplement:
 - Total number of tablets taken

- Subject compliance with study medication dosing as determined by self-reported administration reports and supplement reconciliation
- Reason for dose change, if applicable. Any AE(s) precipitating a dose reduction must be reported even the minimum AE reporting threshold is not otherwise met ([Section 9.2](#)).
- Anti-neoplastic treatment delay(s):
 - Total number of days delayed from planned schedule
 - Cause for delay: AE, or reason other than AE
- Anti-neoplastic agent dose reduction(s):
 - Delayed agent(s)
 - Planned dose(s)
 - Actual dose(s)
 - Cause for dose change: AE, or reason other than AE
- All unplanned or prolonged hospitalizations due to (an) AE(s) ([Section 9.1.9](#)):
 - Date of admission or start of prolongation and discharge date
 - Causes/diagnoses precipitating hospitalization or prolonged hospitalization
- Concomitant medication review at each scheduled visit for the following:

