9.2 Required Reporting

9.2.1 UVa Cancer Center DSMC Reporting Requirements

All AEs must be reported into UVa Cancer Center OnCore database within the time frame specified below. All timeframes are expressed in (calendar) days from the first point at which any member of the study team learned of the event.

For the purposes of reporting AEs for DSMC review, expectedness is defined in relationship to treatment with the investigational agent. I.e. Is the AE in question expected when undergoing genistein treatment? See Sections [5.1.7](#) and [5.2.4](#) for the expected AE. AEs meeting the thresholds below require additional reporting in OnCore beyond the routine data capture associated with a reporting period.

Target AEs do not need to be reported apart from routine data capture unless they meet the criteria below. Progressions, recurrences, and secondary malignancies must be reported within 30 days of the end of the reporting period during which they occurred, or the next quarterly deadline, whichever comes last. See the Procedure Manual for additional information pertaining to data capture.

Table 5. DSMC reporting requirements for AEs that occur during Cycles 1 – 4

Attribution to Study Supplement	Grades 1 & 2		Grade 3		Grade 4	Grade 5
	Expected & Unexpected		Expected & Unexpected		Unexpected	Unexpected
	Target AEs ¹	All other:	Target AEs ¹	All other:		
Unrelated	OnCore: 30 days/quarterly ³	Not required	OnCore: 30 days/quarterly ³	Not required	OnCore: 30 days/quarterly ³	See SAE
Unlikely				OnCore: 30 days from end of Cycle		
Possible				OnCore: 15 days from end of Cycle		
Probable						
Definite						
SAE ⁴	OnCore: (24-hrs), 7 days ²					

¹ Target AEs: Neutrophil count decreased, infection (any), mucositis oral, febrile neutropenia, fever, tinnitus & hearing impaired (subjects on platinum-based chemotherapy only), peripheral

motor neuropathy (subjects on vincristine only).
² Enter into Cancer Center database within 24 hours and submit supporting documentation within 7 days.
³ Data to be entered within 30 days of the end of the reporting period or the next quarterly deadline, whichever comes last. Deadlines are Jan. 31, Apr. 31, July 31, and Oct. 31.
⁴ Any AE that is an SAE must be reported using the SAE timeline regardless of grade or attribution.

Less stringent reporting is required during the follow-up period.

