10.1 Data Collection/CRF Completion

All data must be entered into OnCore in accordance the University of Virginia Cancer Center OnCore standard operating procedure (SOP), which can be found on the OnCore Resources page (see the OnCore Help tab). AEs must be entered into OnCore as described in [Section 9.2](#) and in the Procedure Manual. All other study specific data must be entered into OnCore in the timeframes specified in the SOP. Sample CRFs are available in the Procedure Manual appendices.

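### Abdominal pain, the only adverse event expected from genistein, is not a target AE, so its recorded low-grade incidence would be understated and filtered by attribution

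*Combined protocol and SAP*

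**What the plan says.** On expected effects, Section 5.1.7 states: "The most common effect is abdominal pain (≤ grade 2). This is the only AE that will be considered to be expected".

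The target AEs appear in 6.2, 6.3 and Table 5 footnote 1. The footnote reads "Target AEs: Neutrophil count decreased, infection (any), mucositis oral, febrile neutropenia, fever, tinnitus & hearing impaired" and adds peripheral motor neuropathy for subjects on vincristine. For grade 1 and 2 events in Cycles 1 to 4, Table 5 requires OnCore entry of target AEs and marks all other events as not required. SAEs are reported at any grade or attribution. At baseline, 6.2.1 asks for every grade of the target AEs but for other conditions only from grade 3 upwards.

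One rule overrides the threshold. Section 6.3 says: "Any AE(s) precipitating a dose reduction must be reported even the minimum AE reporting threshold is not otherwise met". In 4.7.4, Table 1 prescribes a supplement dose reduction for a grade 2 event that is at least possibly treatment-related.

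Other wording is broader. Section 9 has all AEs collected, in the manner the later sections describe, and recorded in the medical and study records. Section 9.2.1 opens by sending all AEs to OnCore, then says "AEs meeting the thresholds below require additional reporting in OnCore beyond the routine data capture associated with a reporting period". Section 10.1 says "AEs must be entered into OnCore as described in" Section 9.2 and the Procedure Manual. Section 10.2 has the DSMC review all AEs.

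On the use of these data, the synopsis says "Safety will be assessed by incidence and severity of AEs and changes in physical examinations", and its statistical methods promise a comparison of safety data between genistein and placebo cycles.

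**The concern.** The target list consists of chemotherapy toxicities and of infection and fever outcomes, which genistein is hoped to reduce. It does not include the one effect that the protocol expects genistein to cause. Section 1.3 gives safety in pediatric cancer patients as a purpose of the study and calls existing data scant.

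Chemotherapy also causes abdominal pain, so an investigator who sees mild pain cannot tell which agent is responsible. Randomised order and placebo cycles exist to separate the two causes without that judgement. If low-grade pain reaches the database only after it has been judged possibly related to the supplement, the attribution-free comparison is lost and part of the incidence goes unrecorded. A low count in the final report would then be hard to interpret.

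**Working it through.** The plan states no figure on this point, so there is nothing to reproduce. The check traces the capture rules by grade and attribution, then illustrates the scale.

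**Step 1: what must reach OnCore for non-serious abdominal pain in Cycles 1 to 4**

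| Grade | Attribution to supplement | OnCore entry | Source |
|---|---|---|---|
| 1 | any | not required | Table 5, non-target column |
| 2 | unrelated, unlikely | not required | Table 5, non-target column |
| 2 | possible, probable, definite | required | 4.7.4 Table 1 triggers a dose reduction; 6.3 then requires the report |

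At baseline, grades 1 and 2 are not required either (6.2.1).

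**Step 2: does the Table 5 entry cover every attribution?** It is printed once, on the unrelated row, and reads as a merged cell. That is an inference from layout, but two other sections support it. Section 9.2.3.3 describes the target AEs gathered only for endpoint analysis as non-serious grades 1 and 2 at any attribution, plus non-serious grade 3 judged unrelated or unlikely. That description makes sense only if low-grade events outside the target list are not otherwise collected. Section 9.2.3.1 makes collection regardless of severity or attribution a special feature of target AEs.

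**Step 3: does the all-AE wording override Table 5?** Not clearly. Section 9 defers to the sections that follow it, and 9.1.1 limits reporting to clinically significant events. Section 9.2.1 refers to routine data capture, but the per-cycle list in 6.3 does not name abdominal pain.

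**Step 4: how likely is attribution elsewhere?** Appendix C marks abdominal pain for actinomycin, cyclophosphamide, daunorubicin, doxorubicin, etoposide and topotecan (6 of the 9 qualifying agents) and for vincristine. It is not marked for carboplatin, cisplatin or ifosfamide.

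**Step 5: illustration.** The 44 subjects come from 8.2; each is planned to receive both genistein and placebo. Let q be the share of cases that are grade 2 and judged at least possibly related. Then recorded incidence = true incidence × q. The true incidences and q are assumptions; the documents give neither.

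- True 20%: 44 × 0.20 = 8.8 cases. Recorded: 0 at q = 0; 8.8 × 0.25 = 2.2 (5%) at q = 0.25; 4.4 (10%) at q = 0.5; 8.8 at q = 1.
- True 10% to 30% at q = 0.25: 4.4 to 13.2 cases become 1.1 to 3.3, a recorded incidence of 2.5% to 7.5%.
- Contrast, if q is equal in both periods: true 30% against 20% is 10 points; recorded at q = 0.25 it is 7.5% against 5%, or 2.5 points. The ratio is preserved, but there are fewer events.

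**Step 6: precision with full capture.** Exact 95% intervals: 9/44 gives 9.8% to 35.3%; 0/44 has an upper limit of 8.0%.

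**The case against.** The strongest reply is that the comparison survives. Attribution is made blind (4.6), the same rule applies to genistein and placebo, and 4.7.4 restarts the supplement at full dose in Cycle 3, so the dose-reduction trigger works in both periods. Related grade 2 pain can be estimated and compared, and SAEs are captured at any grade. This stands. A reader might infer that the trial cannot estimate the incidence of abdominal pain at all, or has no blinded comparison of it; the documents do not support either reading.

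Second, an event that need not be entered may still be entered. The Procedure Manual and sample CRFs, to which the protocol sends data-capture detail, are not among the documents and could ask for more. This also stands, so it would be wrong to say that grade 1 pain never reaches the database. The text supports only that no section clearly requires it.

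Third, the contrast for abdominal pain in the Appendix B fact sheet (year 1: 2.2% against 1.1%) is small, and comes from postmenopausal women who all took calcium and vitamin D3. A reader might infer that the collection rule would hide such a difference. It is 44 × 0.011 = 0.48 of a subject, which full capture could not resolve either. The case rests on unbiased description, not on power.

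Fourth, the formal objectives in Section 2 include no estimate of genistein toxicity, and limiting low-grade reporting is a defensible economy in a pilot. That explains a general threshold. It does not explain applying the threshold to the one expected effect, given the safety comparison in the synopsis.

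A reader might also extend the point to estrogenic effects. Section 5.1.7 says only that genistein may have estrogenic properties and could worsen estrogen-sensitive conditions, which exclusion criterion 15 keeps out. That is too little to support a request here.

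**Conclusion.** The point holds as a gap in safety data capture. Non-serious grade 1 abdominal pain, and grade 2 pain judged unlikely or unrelated, need not be entered in OnCore. The recorded incidence of grade 2 or lower pain would therefore be understated by an amount that depends on blinded attribution, and the planned genistein-versus-placebo safety comparison would be incomplete, though not absent, for the one expected effect.

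The size of the loss cannot be derived from the documents; the figures in step 5 only show how it scales with q. The conclusion rests on reading the Table 5 entry as covering all attributions, which 9.2.3.3 supports, and on the Procedure Manual not adding a requirement. The primary endpoint is unaffected. The change is worth making because it is cheap and because the protocol contradicts itself on whether all AEs go to OnCore.

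**What to change.** - Add abdominal pain to the target AEs in 6.2, 6.3 and Table 5 footnote 1, with baseline grade and maximum grade per cycle, at any attribution.
- State in 8.4 that it will be summarised by genistein and placebo cycles.
- Reconcile the statements in Section 9 and 9.2.1 that all AEs are collected and reported in OnCore with the Table 5 entry that exempts non-target grade 1 and 2 events. Say plainly what routine data capture includes.
- Say in 9.2.3.3 that abdominal pain is not among the target AEs left out of the annual FDA report. Otherwise the new listing would also remove non-serious related grade 2 events from that report.

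The cost is a short amendment and about one CRF field at baseline and per cycle: 44 × (1 + 4) = 220 entries if all subjects complete four cycles. The weekly visits already include a symptom-directed examination and AE review. Estimates would remain imprecise with 44 subjects, as the intervals in step 6 show.

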9.2.2 IRB Reporting Requirements

Serious and unexpected AEs must be submitted to the site IRB according to the participating site institutional policies.

For the UVa clinical site, the PI or designee is responsible for reporting AEs and unanticipated problems to the UVa Institutional Review Board for Health Sciences Research (UVa IRB-HSR) according to the following guidelines.

For the purposes of reporting to UVa IRB-HSR, expectedness is defined in relationship to the patient population. I.e. Is the AE in question expected given the characteristics of the population being studied or in terms of the nature, severity or frequency given the research procedures described in the protocol?

Table 7. IRB Reporting Requirements for UVa

Type of Event	To whom will it be reported:	Time Frame for Reporting	How reported?
Any internal event resulting in death that is deemed DEFINITELY related to (caused by) study participation An internal event is one that occurs in a subject enrolled in a UVa protocol	IRB-HSR	Within 24 hours	IRB Online and phone call www.irb.virginia.edu/
Internal, Serious, Unexpected AE See also OnCore reporting requirement (Section 9.2.3.2, Procedure Manual).	IRB-HSR	Within 7 calendar days from the time the study team received knowledge of the event. Timeline includes submission of signed hardcopy of AE form.	IRB Online www.irb.virginia.edu/
External, Serious, Unexpected AE that results in a change to the risk section of the consent and/or modification to the protocol	IRB-HSR		IRB Online www.irb.virginia.edu/
Unanticipated Problems that are not AEs or protocol violations This would include a Data Breach.	IRB-HSR	Within 7 calendar days from the time the study team received knowledge of the event.	Unanticipated Problem report form. http://www.virginia.edu/vprgs/irb/HSR_docs/Forms/Reporting_Requirements-Unanticipated_Problems.doc
Protocol Violations (The IRB-HSR only requires that MAJOR violation be reported, unless otherwise required by your sponsor, if applicable.)	IRB-HSR	Within 7 calendar days from the time the study team received knowledge of the event.	Protocol Violation and Enrollment Exception Reporting Form http://www.virginia.edu/vprgs/irb/hsr_forms.html
Data Breach	The UVa Corporate Compliance and Privacy Office ITC: if breach involves electronic data UVa Police if breach includes such things as stolen computers.	As soon as possible and no later than 24 hours from the time the incident is identified. As soon as possible but no later than 24 hours from the time the incident is identified. IMMEDIATELY.	UVa Corporate Compliance and Privacy Office: [contact] ITC: Information Security Incident Reporting procedure, http://www.itc.virginia.edu/security/reporting.html [contact]

Table 8. DSMC Reporting Requirements

INDEPENDENT DSMB/DSMC			
DSMB/DSMC Reports	IRB	15 calendar days of the study team receiving the report	Copy of DSMB/DSMC report

9.2.3 Additional reporting Requirements

9.2.3.1 Target Adverse Events

Target AEs are AEs of special interest and will be collected throughout the treatment phase, regardless of expectedness, severity, or attribution. They are listed in [Section 6.3](#). Target AEs will not be collected during the follow-up reporting periods unless the AEs otherwise meet the DSMC or IRB reporting requirements outlined in [Sections 9.2.1](#) and [9.2.2](#).

9.2.3.2 Additional Reporting Requirements for Affiliate Sites

In addition to reporting in OnCore, all SAEs must be reported by facsimile within 24 hours of the event to the Sponsor (UVa) as outlined in the Procedure Manual. Any SAEs that occur in the 30 days following the last dose of protocol therapy must be reported. After that time, only SAEs that are related to protocol therapy are required to be reported. For every SAE which occurs, affiliates must send an SAE report with the following information:

- Safety reporting cover sheet (Procedure Manual appendices)
- Relevant hospital case records and autopsy reports (where applicable)

